# **Hair Care Product Use Among Women Of Color: A Northern Manhattan Intervention**

**NCT04493892**

**09/21/2022**

## Background

Recent trends suggest a convergence in breast cancer (BC) incidence rates in black and white women due to the stability in incidence trends in white women compared to the steady annual increase in black women (0.3% per year) (1,2). These changing incidence patterns over a short time period cannot be attributed to changing genetic factors. While reproductive trends have been proposed to drive some of the health disparities,(3) endocrine disruptor chemical (EDC) exposures during BC susceptibility windows may also play a role in breast cancer health disparities (4,5) as EDC exposure patterns differ by race and ethnicity (6,7).EDCs disrupt reproductive development and increase cancer risk through their ability to have a direct, indirect, or interactive action on cellular processes within the mammary tissues. These actions include, but are not limited to, acting upon hormone receptors, the ability to behave agonistically or antagonistically on nuclear receptors, and confer epigenetic changes that increase oncogenic susceptibility (8-11). EDCs may have the most influence during periods of dynamic structural and functional changes in the mammary glands, (4,5,12) such as during pregnancy and the postpartum windows (5,13).

Hair care products (HCPs) are a class of personal care products (PCPs) that contain EDCs; there are stark differences in HCP use by race (6,14-17). In a group of racially and ethnically diverse women (n=301), compared to non-Hispanic white women, women of African descent were more frequent users of hair oils, lotions, leave-in conditioner, root stimulator and perm/relaxers (14). The Sister Study has also shown where 67% of Black women were users of hair pomades and straighteners, only 3% of White women were users (7). Differences in hair texture may explain differences in use. Nevertheless, of major concern, clinical, epidemiological, and laboratory studies have suggested HCPs are associated with earlier pubertal events, (6,18-21) where the timing of pubertal maturation is an established risk factor for BC risk (22-24). Additional studies have shown that compared to infrequent users, women classified as moderate or frequent users of PCPs had a 10-15% higher BC risk,(25) dark hair dye is associated with a 52-72% increased BC risk, (17,26) a history of chemical relaxer or straightener use is associated with a 64-74% increase in BC risk, (17,27) and in 454 Mexican women (233 cases) urinary concentrations of monoethyl phthalate (MEP) were positively associated with BC [OR 2.2. (1.33, 3.63)], with stronger associations observed for pre-menopausal women [OR 4.1. (1.6, 10.7)] (28).

Evidence is emerging on EDC exposures across the pregnancy/postpartum periods. This is of importance because while pregnancy is associated with a long-term reduced risk of BC, it also confers an increased risk of BC for at least a decade after birth (1,2,8,9). EDC exposure during this period of increased risk could promote ‘activation’ effects for BC following pregnancy. In pregnant women, PCP use is correlated with higher concentrations of urinary phthalates, (29-31) urinary metabolite concentrations vary by PCP type,(32,33) and urinary metabolite concentrations differ by sociodemographic factors and across racial and ethnic populations (34). For example, a multiethnic cohort of 446 pregnant women found that urinary phthalate metabolites were significantly higher among WOC (34). However, while studies assess knowledge and attitudes of PCPs during the pregnancy/postpartum periods, no study has implemented a behavioral intervention. Five cross-sectional studies have examined knowledge,

attitudes, and prevention behaviors in pregnant women. Four studies with women of French descent focused on intent to change cosmetic use during pregnancy (32,35-37) and TIDES, a US based pregnancy cohort (n=894), surveyed health attitudes around PCP use (38).

These studies are not reflective of PCP practices among pregnant WOC. An intervention to reduce phthalate exposures during the pregnancy/postpartum window would have both fetal/early and maternal health implications. First, behavioral changes during pregnancy could mitigate EDC exposures that exert in utero effects that may program long term risk for hormone-related disease for the child. Second, behavioral changes could reduce ‘activation’ effects for BC following pregnancy (12). Pregnant women are primed to change behaviors for their babies’ health. Therefore, we propose an educational intervention during pregnancy to promote reduced use of phthalate-containing HCPs. We focus on phthalates because of the well documented animal (39,40) and human (41-45) evidence on their effects on reproductive health and development, (11,41) they are ubiquitous and added to HCPs to provide scent, (6,19) detected in human breast milk, urine, amniotic fluid and placenta (suggesting fetal exposure), (11,41) and phthalate interventions have proven successful (47-49).

## **Study Design**

### **Objective:**

To reduce use of personal care products that contain endocrine disrupting chemicals among women. For this pilot intervention, we focus on the hair care product class of personal care products, the reduction in use of phthalate-containing Hair Care Products (HCPs) and use among pregnant Women of Color (WOC).

### **Study Aims:**

This pilot interventional study will include prospective data collection, including questionnaire data and urinary metabolite measures. We will also conduct key informant sessions and interviews and focus groups. This pilot proposal will apply the Precaution Adoption Process Model (PAPM), a 7-stage theoretical model for health behavior change that attempts to explain how an individual comes to decisions to take action and how the individual then translates that decision into action (Glanz K, et al. Health Behavior and Health Education: 4th Ed.; 2008).

Therefore, among WOC, defined as Black or Hispanic women, residing in Manhattan, Bronx, Queens, Brooklyn, and Staten Island and in the 3rd trimester of pregnancy, we propose the following:

### **Specific Aims:**

1. Qualitative Approaches across 5-10 groups (n=50-100 total participants), we will:

- a. Deliver an educational intervention on harmful chemical exposures, such as phthalates, found in hair care products, developed by the research team using empirical evidence with key informant feedback.

b. Through focus groups gather participant feedback on content and questions pertaining to intervention and attributes women of color consider when deciding on Hair Care Product use, using a semi-structured guide.

2. Quantitative Approaches using repeat measures, we will:

- a. Using repeated questionnaires to assess PAPM stages, we will assess self-reported behavioral changes in the use of phthalate-free hair care products comparing stage at enrollment to
  - Stage after the intervention (post-test1),
  - Stage at 1- month post-intervention (post-test2), and
  - Stage at 1-month postpartum (post-test3).
- b. Examine the correlation between self-reported behavioral change assessed by the PAPM questionnaire and
  - Change in self-reported Hair Care Product exposure measured via questionnaire (n=50),
  - Change in internal dose of urinary phthalate metabolites (targeted gas chromatography/high resolution mass spectrometry (known as GC/HRMS) Orbitrap; n=25 with 3-repeat samples),
  - (Exploratory) change in internal dose of all-other detectable urinary metabolites (untargeted GC/HRMS-Orbitrap; n=25 with 3-repeat samples).

#### Remote Option for Study Aims:

We have included a description of how each element of the protocol will be administered if remote is necessary.

**Hypothesis:** We hypothesize that the pilot intervention will increase awareness of phthalate chemicals in hair care products and women progressing across the PAPM stages. We expect an inverse association between participants who adopt the use of phthalate-free hair care products and self-reported phthalate-containing hair care products and urinary phthalate concentrations. We compare phthalate concentrations in the 3rd trimester when catabolic activity peaks (Zeng et al. Annals of Nutrition and Metabolism. 2017;70(1):59-65) and subsequently measure sustained behavioral changes 1-month postpartum. We will explore metabolite concentrations across the whole period recognizing the possible limitation of changes in metabolism across the follow-up period.

#### Potential Risks

This is a minimum risk protocol. Participants will receive the following information about potential risks on the consent form:

*Participants may feel uncomfortable answering some of the questions on the questionnaires, but they have been informed that they have the right to refuse to respond to any questions they do not wish to answer. They are informed that the information they provide on the questionnaire will be*

*kept entirely confidential. However, any time personal information is released, there is a possibility of confidentiality being compromised.*

We have provided participants with the following information about the potential for a breach in confidentiality on the consent form:

*Despite all of our efforts, unanticipated problems, such as a stolen computer may occur, although highly unlikely. Please note the following process will be adhered to for ANY and ALL aspects of the study in which your research data is labeled with your unique code number (aka study ID): Your unique code number (aka study ID) will be separated from your name or any of your information that could identify you. The research file that links your name to the code number will be kept in a locked file cabinet and / or an encrypted data file and only the investigator and study staff will have access to the file. Your name or any of your information that can identify you will not be used in any reporting of the study results.*

## **Potential Benefits**

There are no direct benefits to participation. The consent form states, “You may or may not receive personal benefit from taking place in this study.”

Participants can choose not to participate in any parts of the study or can choose to withdraw from the study at any time. This study does not present greater than minimal risk.

## **Subject Population Justification**

This study concerns health risks for pregnant women associated with increased levels of EDC chemicals through the use of personal care products that contain EDCs. EDCs may have the most influence during periods of dynamic structural and functional changes in the mammary glands (4,5,12) such as during pregnancy and the postpartum windows (5,13). This is important because pregnancy confers an increased risk of breast cancer for at least a decade after birth (1,2,8,9). EDC exposure during this period of increased risk could affect the fetus and promote ‘activation’ effects for BC following pregnancy. An intervention during pregnancy on EDC exposures and HCPs could have intergenerational health implications for mother and child, which is why we are targeting pregnant women. We are obtaining remote e-consent from this vulnerable population due to restrictions posed by the COVID-19 pandemic.

## **Statistical Procedures**

For the Pilot Intervention:

Aim 1 Analysis. All sessions (whether conducted in person or remote via Zoom) will be recorded and transcribed verbatim by a professional transcription service. We will use Dedoose to code using grounded theory and qualitative content analysis focusing on the questions and content feedback of the educational intervention and attributes pertaining to PCP use. [name] will oversee the creation of the codebook and train the research staff involved in coding transcripts. We believe with n=50-100, we will meet our goal of saturation and finalized thematic codes will aid in improving the educational intervention and provide an exhaustive categorization of attributes WOC consider for HCP product selection.

**Aim 2b Analysis:** Please see Study Procedures section (under ‘Metabolomics’ heading) for an explanation of [name] and his team at Brown University’s involvement in the analysis portion of this study. In brief, this exploratory analysis, performed by our partner collaborators at Brown University, will conduct Hair Care Product descriptive analyses, including the frequency of phthalate-containing products, by category and overall. They will conduct urinary phthalate descriptive analyses (log transformed concentrations) comparing detectable ranges for each of the urinary phthalate exposure constructs and comparing with national levels from biomonitoring reports. They will also conduct untargeted descriptive analyses by characterizing the patterns in chemical exposures over time through principle component analyses (PCA) (Gibson et al. Current environ health reports. 2019;6(2):53-61). Using spearman correlations, they will independently examine the correlation between PAPM and a) change in phthalate containing PCPs, and b) change in PCA patterns. **Results:** We expect the intervention will result in an association between PAPM progresses and a decreased use of phthalate-containing HCPs and lower concentration levels of MEP (and LMW metabolites).

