Hair Care Product Questionnaire: Asking participants to take stock of current / recent and past hair care product use. This questionnaire was developed by our colleagues at the Rutgers Center for Environmental Exposures and Disease based on / modified from the Women's Circle of Health Study questionnaire that captured a detailed list (including brand name and product) of each hair product each participant used in the last 24-48 hours. This questionnaire is best completed in the space where the woman conducts her everyday hair care routine as she will need to recall product type and name. Therefore, we are sending the questionnaire to be completed at home prior to the educational intervention.

Precaution Adoption Process Model Questionnaire: A 7-stage theoretical model for health behavior change that attempts to explain how an individual comes to decisions to act and how the individual then translates that decision into action. The 'change in PAPM variable' (PAPM) will illustrate how the intervention moves people across staging. Given movement can be fluid, (Rouillon et al. Int J Environ Res Public Health. 2018;15(10), participants will be categorized as progresses (i.e. advancing stage(s) from last reported stage), regresses (i.e. regressing stage(s) from last reported stage), or stagnant (i.e. not moving from last reported step), comparing: pre-test to post-test1, post-test1 to post-test2, and post-test2 to post-test3, and post-test1 to post-test3. Those who progress to Stage 4 will be labeled as negative progresses. We will provide descriptive statistics by pre-test, post-tests, and by the PAPM variable at each time point (when relevant). Using spearman correlations, we will examine independent correlations between PAPM stage at pre-test with each post-test (post-tests1-3). While PAPM staging is not a continuous parameter but ordinal, (Glanz et al. Health Behavior and Health Education: Theory, Research and Practice 4th Edition; 2008) correlations will inform how the intervention moves people across staging.

The PAPM stages for this study are described as follows:

Stage 1: Never heard of endocrine disrupting chemicals (EDCs), nor EDCs in hair care products (HCPs)

Stage 2: Never thought about using phthalate-free HCPs

Stage 3: Undecided about phthalate-free HCPs

Stage 4: Decided not to use phthalate-free HCPs

Stage 5: Decided to use phthalate-free HCPs

Stage 6: Procured and has used (at least once) phthalate-free HCPs

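### The exposure hypothesis concerns women who adopt phthalate-free products, but the Aim 2b variable counts almost any stage advance as progress, which can pull the correlation toward zero

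*Combined protocol and SAP*

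**What the plan says.** The hypothesis (Remote Option for Study Aims) has two halves. One is about stage movement: "the pilot intervention will increase awareness of phthalate chemicals in hair care products and women progressing across the PAPM stages". The other is about exposure and names a narrower group: "We expect an inverse association between participants who adopt the use of phthalate-free hair care products and self-reported phthalate-containing hair care products". The same is expected for phthalate levels in urine.

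The analysis variable is defined in Procedures, Specific Aims, in the paragraph on the PAPM questionnaire: "The 'change in PAPM variable' (PAPM) will illustrate how the intervention moves people across staging". There, "participants will be categorized as progresses (i.e. advancing stage(s) from last reported stage"; the other categories are regresses and stagnant. One kind of advance is set apart: "Those who progress to Stage 4 will be labeled as negative progresses". In the stage list, Stages 1 to 3 run from unaware to undecided, Stage 4 is a decision against, and the next is "Stage 5: Decided to use phthalate-free HCPs". Use first appears at Stage 6 (at least once) and becomes regular at Stage 7.

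The Aim 2b paragraph of Statistical Procedures, which calls the analysis exploratory, plans Spearman correlations between PAPM and change in exposure. It gives the expected result as "We expect the intervention will result in an association between PAPM progresses and a decreased use of phthalate-containing HCPs", together with lower urinary metabolite levels. The specific aims give n=50 for the questionnaire exposure and n=25 for urine. Nowhere do the documents define an adopter or plan an analysis by reaching Stage 6 or 7.

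**The concern.** Aim 2b is the planned check that self-reported behaviour change is matched by lower exposure. The exposure half of the hypothesis is about adoption, while the variable carrying the test is advancement. A woman who goes from unaware to undecided, or from undecided to decided, is a progress, as is a woman who starts regular use. If the first two do not change what they put on their hair, they sit in the progress group with no fall in exposure and weaken the correlation.

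A correlation near zero would then be hard to read. It could mean that adoption does not lower exposure, or that most women who progressed had not yet adopted.

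**Working it through.** The plan states no expected correlation, significance level, power or stage distribution, so there is no figure of its own to reproduce.

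**Step 1: count the forward moves.** Seven stages allow 7 × 6 / 2 = 21 upward moves.

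| End of move | Moves | Count | Label |
|---|---|---|---|
| Stage 4 | 1-4, 2-4, 3-4 | 3 | negative progress |
| Stage 2, 3 or 5 | 1-2, 1-3, 2-3, 1-5, 2-5, 3-5, 4-5 | 7 | progress, no use implied |
| Stage 6 or 7, from Stage 5 or below | five starts × two ends | 10 | progress, new use |
| Stage 7 from Stage 6 | 6-7 | 1 | progress, already a user |

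Ordinary progresses number 21 − 3 = 18, and 7 of these involve no use. These are counts of move types, not shares of women.

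**Step 2: try the other reading of PAPM.** If the correlation used the number of stages moved, 1-to-5 would be four steps with no use and 5-to-6 one step with first use. The first would outrank the second, so that coding does not track adoption either.

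**Step 3: compare the intervals.** Exposure is measured before the session (Phase III) and at the two follow-ups (Phase V). Post-test1 is given at the end of the session and has no exposure measurement of its own. The change categories are planned for pre-test to post-test1, post-test1 to post-test2, post-test2 to post-test3, and post-test1 to post-test3. None of these spans pre-session to follow-up, and the Aim 2b paragraph does not say which one enters the correlation.

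**Step 4: size, on assumed shares.** Let pP be the proportion who progress and pA the proportion who adopt, with adopters a subset of progressors. If exposure depends on adoption only, then

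corr(progress, exposure change) = corr(adoption, exposure change) × √[pA(1 − pP) / (pP(1 − pA))].

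This holds for Spearman with a yes/no variable. With pP = 0.60 (assumed):

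| Progressors who adopt (assumed) | pA | Factor | A correlation of −0.50 becomes |
|---|---|---|---|
| 25% | 0.15 | √(0.06/0.51) = 0.34 | −0.17 |
| 50% | 0.30 | √(0.12/0.42) = 0.53 | −0.27 |
| 75% | 0.45 | √(0.18/0.33) = 0.74 | −0.37 |
| 100% | 0.60 | 1 | −0.50 |

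For scale, the 95% half-width near zero is tanh(1.96 × √(1.06/(n − 3))): 0.29 at n=50 and 0.41 at n=25. The −0.27 is only just inside the first of these.

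**Step 5: cross-check by simulation.** Assume 50% progress, half of them adopt, adopters' exposure falls by 1.2 SD and nobody else's changes. Spearman's rho is −0.26 with any progress and −0.45 with adoption. The formula agrees: √(0.125/0.375) = 0.58, and 0.58 × −0.45 = −0.26. At an assumed two-sided 5% level, power is 43% against 90% at n=50, and 23% against 60% at n=25.

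**The case against.** The strongest counter-arguments are these.

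- **The coding is not stated outright.** The Spearman sentence says only PAPM. Reading it as the change category rests on the definition in Procedures and on the expected-result wording. A reader might infer that 1-to-2 is certainly scored the same as 1-to-7; the documents do not support that. The mismatch remains, because counting stages moved does not track adoption either (step 2).
- **Not every advance is pooled.** A reader might infer that progress of any kind counts alike. Moves into Stage 4 are labelled apart, although how they enter the correlation is not said. Stage progression is itself part of the hypothesis, so the mismatch concerns only the exposure half.
- **No exposure change below Stage 6 is an assumption.** The outcome is use of phthalate-containing products, and a woman could cut down on those without buying a phthalate-free one. This stands, and the dilution is conditional on it.
- **Awareness-only moves may be rare.** The urine subsample is prioritised on post-test1 to post-test3, after the education. From Stages 3 to 6 there are 9 ordinary progresses, of which only 2 (3-5, 4-5) involve no use. Free samples or a $10 card also make Stage 6 easier to reach. The second point has some force. The first is weaker, because a change matched to the exposure measurements starts at pre-test, when the early stages can still be occupied.
- **A bare adopted/not-adopted indicator has faults too.** It would score 6-to-7 moves and drops out of use as no change. This stands and is why an ordered variable is proposed. Pooling one-time with regular use remains a weakness.

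**Conclusion.** The mismatch is in the text: the exposure hypothesis is about adopters, the Aim 2b variable is about advancement, and 7 of the 18 ordinary progress types stop short of use. The direction of the effect, toward zero, follows if women who move only in awareness or intention keep their exposure unchanged. The size cannot be derived from the documents. The factors 0.34, 0.53 and 0.74 rest on assumed shares and on a yes/no progress variable that leaves out regresses and negative progresses.

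Two stronger conclusions should not be drawn. One is that 7 in 18 women would be misclassified; the counts are of move types. The other is that the study would fail its main test. The analysis is labelled exploratory in a pilot with no stated level or power, and stages are recorded at every time point, so adopters stay identifiable. What is at stake is whether the correlation can be interpreted. The change is worth making because it is cheap and fits the plan's own hypothesis.

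**What to change.** In the Aim 2b paragraph of Statistical Procedures:

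1. Prespecify an ordered adoption-change variable: moved into use (Stage 5 or below to Stage 6 or 7), no change in use status, moved out of use (Stage 6 or 7 to Stage 5 or below). This also settles how moves into Stage 4 are scored.
2. Measure it from pre-test to post-test2 and from pre-test to post-test3, and correlate each with the exposure change over the same interval.
3. Report women already at Stage 6 or 7 at pre-test separately, including 6-to-7 moves, since no change in their case means continued use.
4. Keep progresses, regresses and stagnant for Aim 2a and as a secondary Aim 2b analysis.
5. Report the number of adopters and a confidence interval beside each correlation.

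The cost is wording only, with no new data. The downside is imprecision if few women adopt: at 15% adoption there would be about 0.15 × 25 ≈ 4 adopters in the urine sample.
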